Aim 2: Determine the response rates; defined as the proportion of participants who complete all three days of diet assessments with energy intake >600 kcal, either through KeenoaTM or ASA24. We hypothesize that Keenoa will have higher response rate for those completing 3-day diet records.

Methods

We will conduct a randomized block trial, recruiting participants from the Third Generation-based cohorts, at their fourth examination. For the purpose of this trial, we will randomize the dietary assessment tool weekly between ASA24 and KeenoaTM, therefore, depending on the week of administration, participants are randomized to either a 3-day dietary record via ASA24 or KeenoaTM. Refer to **Figure 1** for complete description of enrollment process.

During the weeks when KeenoaTM is administered: we will ask the participants if they have a smartphone. If not, individuals will not be eligible to participate in the trial, but they can still complete ASA24 dietary records, allowing their dietary information be collected for the FHS Glucose Monitoring Study. Then we will ask participants if they have a Google Play ID (for Android users) or Apple ID (for IOS users). If yes, our research technician at FHS center will help participants in setting up KeenoaTM. If not, we will provide participants with at home instruction protocol.

Statistical Analysis Plan

Power calculation: We estimate that we will require ~50 participants per group to complete aims 1 and 2.

Over the first 8 months of the current exam, we have had a response rate of 62.1% of participants completing 3 days of diet record using ASA24. We estimate that KeenoaTM would have an 80% response rate among our participants, therefore, considering alpha=.05, and 80% power, the sample size required is 50 participants per group.

Aim 1 analysis:

We will use chi-square to evaluate whether the average satisfaction rate (out of 5) of the two instruments (Keenoa vs. ASA24) is statistically significantly different.

Aim 2 analysis:

We will use chi-square to evaluate whether the response rates, defined as the percentage who completed 3 days of dietary assessment with energy intake >600 kcal, from the two instruments (Keenoa vs. ASA24) are statistically significantly different.

We will generate a summary of participant characteristics using descriptive statistics.

References:

1. Willett W. *Nutritional epidemiology*. Oxford university press; 2012.

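### Each aim is analysed only by a chi-square verdict: no Keenoa-minus-ASA24 difference or confidence interval is planned, and for Aim 1 chi-square does not compare averages

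*Combined protocol and SAP*

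**What the plan says.** All the inferential text is in the Statistical Analysis Plan section of the combined protocol and SAP.

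- **Test for Aim 1:** "We will use chi-square to evaluate whether the average satisfaction rate (out of 5) of the two instruments (Keenoa vs. ASA24) is statistically significantly different".
- **Test for Aim 2:** chi-square again, on whether response rates "from the two instruments (Keenoa vs. ASA24) are statistically significantly different".
- **Aim 2 objective (Specific Aims):** "Determine the response rates; defined as the proportion of participants who complete all three days of diet assessments with energy intake >600 kcal". This implies a rate for each tool, but no contrast between tools.
- **Descriptive statistics:** "We will generate a summary of participant characteristics using descriptive statistics". This covers characteristics, not outcomes.
- **Power calculation:** for ASA24, "we have had a response rate of 62.1% of participants completing 3 days of diet record using ASA24"; Keenoa "would have an 80% response rate among our participants"; and "considering alpha=.05, and 80% power, the sample size required is 50 participants per group".

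The hypotheses under Specific Aims are directional: Keenoa is expected to be more acceptable, and to have the higher response rate. No difference in rates, ratio, mean difference, confidence interval or margin is named anywhere.

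**The concern.** The trial is meant to inform whether Keenoa suits dietary assessment in FHS. That needs the direction and size of any difference and how precisely it is known. A chi-square test supplies a p-value and none of these.

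For Aim 2 the gap is partial. The two rates will be available, so direction can be seen, but the contrast, its precision and its method are not specified in advance.

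For Aim 1 the gap is wider, because the named test does not address the named quantity. Chi-square on a table of tool by score compares the distributions of scores and ignores their order. Chi-square on a dichotomised score needs a cut-point that the plan does not give. Neither compares averages.

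At this sample size a non-significant result is a likely outcome even if the hoped-for gain is real. Without an interval, nothing in the planned output shows how large a difference the data still allow.

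**Working it through.** **Inputs.** From the Power calculation: 62.1% (ASA24), 80% (Keenoa), alpha 0.05, power 80%, 50 per group. From the Methods: tool randomized by week; the opening summary gives 6 weeks in total. Assumed, because not stated: two-sided testing, three weeks per tool, and the SD of satisfaction.

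**1. The plan's own figure.** Two-group formula with pooled variance, mean rate (0.621 + 0.80)/2 = 0.7105:

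n = [1.96·√(2 × 0.7105 × 0.2895) + 0.8416·√(0.621 × 0.379 + 0.80 × 0.20)]² / 0.179² ≈ 100 per group.

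Other two-sided variants give 97 to 111, and one-sided variants 77 to 90. The stated 50 is not reproduced by any two-group variant tried. At 50 per group, two-sided power is about 51% (63% one-sided). The shortfall is a separate point; it matters here because it makes a non-significant result about as likely as not under the plan's own rates.

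**2. Best-case precision for Aim 2 (participants independent).**

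SE = √(0.621 × 0.379/50 + 0.80 × 0.20/50) = 0.0889; half-width = 1.96 × 0.0889 = 17.4 points. At the planned rates the interval is 0.5 to 35.3 points.

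**3. What different results would look like.** ASA24 is set at 31/50 (62%); p-values are from chi-square without continuity correction, and intervals are Newcombe 95%.

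| Keenoa | Difference (points) | p | 95% CI (points) |
|---|---|---|---|
| 31/50 | 0 | 1.0 | -18.4 to 18.4 |
| 36/50 | 10 | 0.29 | -8.3 to 27.4 |
| 39/50 | 16 | 0.08 | -2.0 to 32.7 |
| 40/50 | 18 | 0.047 | 0.2 to 34.4 |

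The first three share one verdict, not significant, and each interval contains 17.9. With 31/50 on ASA24, significance first appears at 40/50, an 18-point gap (41/50 with continuity correction, p = 0.045).

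**4. Allowing for week.** With three weeks per tool, a comparison of weekly results has 3 + 3 - 2 = 4 df and a multiplier of 2.776. With no intra-week correlation the half-width is 2.776 × 0.0889 = 0.247, about 25 points.

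Alternatively, keep 1.96 and apply a design effect with 100/6 ≈ 16.7 participants per week. An assumed ICC of 0.01 gives 1 + 15.7 × 0.01 = 1.16 and a half-width of 17.4 × √1.16 ≈ 18.7 points. An ICC of 0.05 gives 1.78 and about 23.3 points.

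**5. Aim 1.** Half-width for a mean difference, participants independent: 1.96 × SD × √(2/50) = 0.39 SD. For assumed SDs of 0.8 to 1.5 this is 0.31 to 0.59 scale points. With the 4-df multiplier it is 2.776 × 0.2 = 0.555 SD, or 0.44 to 0.83 points.

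**The case against.** The strongest reply is that Aim 2 already commits the trial to producing response rates. The two percentages show direction, and with the group sizes anyone can compute the difference and an individual-level interval. That stands: what is missing for Aim 2 is a pre-specified contrast and its precision, not the raw information. It is only a partial answer, because an interval recomputed from the two percentages would ignore the weekly allocation and tend to be too narrow. It does not help Aim 1, where the test does not match the quantity.

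A second reply is that an interval cannot cure a small sample. This also stands. Identical observed rates would still leave about ±18 points with participants treated as independent, which just includes 17.9. The width is driven by sample size and allocation, and those should not be counted again here.

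A reader might infer more: that FHS would be left unable to tell equal tools from a large difference, or that a non-significant result will be reported as no difference. The documents support neither. Rates by tool are implied, and nothing says how a non-significant result will be worded. Misreading is a risk, not a plan. Nor must the p-value be made secondary: reporting the interval beside the test meets the need.

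**Conclusion.** The point holds as a gap in the planned analysis. Neither aim has a planned between-tool contrast or confidence interval, and for Aim 1 the chi-square test does not compare the averages it is said to compare.

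For Aim 2, at 50 per group and near the planned rates, the 95% half-width is about 17 points at best (independent participants). It is about 25 points with a week-level t interval, assuming three weeks per tool and no intra-week correlation. A non-significant result may therefore be compatible with the 17.9-point gain used for planning. The size of the Aim 1 uncertainty cannot be fixed from the documents, which give no SD.

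This is worth correcting but does not invalidate the Aim 2 test. The sample-size shortfall and the choice of a week-level method are separate issues.

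**What to change.** Amend the two analysis sentences:

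- **Aim 2:** report the Keenoa minus ASA24 difference in response rate with its 95% CI, beside the test.
- **Aim 1:** replace chi-square with the Keenoa minus ASA24 difference in mean satisfaction, its 95% CI and the matching test. The mean is the natural choice because the plan itself names the average as the quantity of interest.
- **Both:** compute the intervals allowing for week of allocation, and state that a non-significant result will be interpreted from the interval and not as evidence of no difference. The 17.9-point planning difference is the only benchmark in the documents against which the Aim 2 interval can be read.

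The cost is a few sentences of SAP text and no new data. It does depend on first choosing a method for week that works with about six weekly units, which the plan does not yet do. The small downside is that the reported intervals will be wide.

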Evaluation of an Artificial Intelligence-Assisted, Image-Based Dietary Assessment Tool in the Framingham Heart Study

NCT06455111

[name]

[contact]

Statistical Analysis Plan pages 3-4

Evaluation of an Artificial Intelligence-Assisted, Image-Based Dietary Assessment Tool in the Framingham Heart Study

Background: Assessment of dietary intake in large, free-living populations is inherently challenging due to the complex nature of human diet. Advancements in traditional methods of dietary assessment (i.e., web-based dietary recalls or records) have aimed at improving data accuracy while reducing participant burden. Further utilizing food recognition technologies to capture real-time food intake may aid in overcoming limitations of existing methods. Keenoa[□], an artificial intelligence-enhanced, image-assisted tool, is a newly designed mobile application that may facilitate collection of dietary data.

Aims: Primarily, we will assess acceptability and usability of Keenoa compared with the traditional, web-based Automatic Self-Administered 24-Hour (ASA24) Dietary Assessment Tool in the Framingham Heart Study Third Generation-based cohorts at examination 4. We will also determine the proportion of participants who complete all three days of dietary assessment with energy intake >600 kcal, either through Keenoa or ASA24.

Methods: With a randomized block design, this study will take place as part of the Framingham Heart Study (FHS) glucose study (R01 DK129305). We currently ask participants from the Third Generation-based cohorts, at their fourth examination, to wear Dexcom G6 Pro continuous glucose monitor on either their arm or abdomen for a duration of at least 4 days. During this time, we request participants to complete 3 consecutive days of dietary record through ASA24. For the purpose of this trial, we will randomize the dietary assessment tool weekly between ASA24 and Keenoa, therefore, depending on the week of administration, participants are randomized to either a 3-day dietary record via ASA24 or a 3-day dietary record through Keenoa. This trial will last a total of 6 weeks.

Background and Rationale

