Keenoa™ is an artificial intelligence-enhanced, image-assisted dietary assessment tool that has been originally designed to facilitate dietary data collection for dietitians and researchers.⁹ Serving as a visual food diary, individuals can upload a picture of their meal, choose the food items eaten using a preselected food list available by the app, and confirm the portion size with the presented visual aids. Two recent trials have aimed to evaluate the validity and usability of Keenoa™ against common methods of dietary assessment.^{10,11} In a randomized controlled trial of 72 Canadian adults, Keenoa™ performed better on analyzing group-level micronutrient intake relative to individual-level intake, suggesting its potential appropriateness for assessing dietary intake of the general population.⁹ In the same study, a greater proportion of participants preferred using Keenoa™ over a traditional pen-and-paper method (34.2% vs. 9.6%).⁹ Another randomized crossover trial with 136 participants showed that Keenoa™ has moderate to strong agreement, when compared against ASA24 recalls, in analyzing energy, macronutrient, and the majority of micronutrient intakes in both healthy adults and those with type 2 diabetes mellitus (T2DM).¹¹ In addition to Keenoa™, several image-based or image-assisted dietary assessment apps have been developed for research purposes.¹² With distinct interfaces, some of these apps, such as the mobile food record (used in All of Us Precision Nutrition study), require uploading pictures from specific distance or angle of the food to ensure precise portion size estimation, which in turn may impose burden on participants. Therefore, selecting proper technology-based instrument relies upon different factors including available resources, study objectives, study population,

etc.,¹² and we chose to assess the acceptability and feasibility of KeenoaTM in order to evaluate dietary habits in the Framingham Heart Study (FHS).

Specific Aims

We will assess the following aims in the FHS Third Generation-based cohort exam 4.

Aim 1: Evaluate acceptability of the Diet Tracking Smartphone Application KeenoaTM, and compare it to that of ASA24 diet records among older adults. We hypothesize that dietary assessment through KeenoaTM is more acceptable than ASA24, using quantitative satisfaction scale (0-5).

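### Both comparisons are unadjusted participant-level tests although the tool is allocated by week over six weeks, so between-week differences in case mix are neither adjusted for nor reflected in the standard errors

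*Combined protocol and SAP*

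**What the plan says.** The Statistical Analysis Plan names one test per aim, a chi-square on the satisfaction score (Aim 1) and a chi-square on the response rate (Aim 2). It closes with "We will generate a summary of participant characteristics using descriptive statistics". No covariate, stratification factor, week term or sensitivity analysis is named anywhere.

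Allocation is by calendar week: "we will randomize the dietary assessment tool weekly between ASA24 and KeenoaTM" (Methods). The summary at the front of the document gives a total duration of six weeks. Aim 1 sets the comparison "compare it to that of ASA24 diet records among older adults".

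The power paragraph rests on a historical ASA24 response rate of 62.1% and an assumed 80% for Keenoa, and concludes: "considering alpha=.05, and 80% power, the sample size required is 50 participants per group".

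**The concern.** Randomising six weeks balances participant characteristics less reliably than randomising about 100 people one at a time. If the age or sex mix varies from week to week and relates to completion or satisfaction, the observed difference between tools carries that variation. A participant-level chi-square treats everyone as independently allocated, so its standard error leaves out the between-week part.

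Age is a reasonable candidate covariate, since one tool is a smartphone app and Aim 1 is framed around older adults. The characteristics are to be tabulated anyway. If no covariates are named beforehand, any adjustment made after seeing that table would be data-driven.

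At stake are some precision in a small trial, and a type I error rate that may exceed the nominal 5%.

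**Working it through.** **Inputs from the documents.** Response rates 62.1% and 80% (difference 17.9 points); alpha 0.05, sidedness not stated; about 50 per group; six weeks.

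**Assumptions, because the documents are silent.** About 100/6 = 16.7 participants per week; the strength of the age effect; the share of age variance lying between weeks (0 or 5%, except where stated).

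**1. The plan's own figure.** Two-sided, pooled variance, mean rate 0.7105:

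n = [1.96 × √(2 × 0.7105 × 0.2895) + 0.842 × √(0.621 × 0.379 + 0.80 × 0.20)]² / 0.179² ≈ 100 per group.

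The stated 50 is not reproduced. A one-sided test needs 79. At 50 per group the power is 50.5% two-sided and 63.1% one-sided.

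**2. Chance imbalance in age.**
- Individual randomisation: SD of the standardised arm difference = √(2/50) = 0.20.
- Week randomisation, 5% of age variance between weeks: 0.20 × √(1 + 15.67 × 0.05) = 0.27.

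**3. What that does to the Aim 2 difference.** The shift is approximately imbalance × ln(OR per SD) × p(1 − p), with p = 0.71. At an odds ratio of 2.0:
- Week randomisation: 0.27 × 0.693 × 0.71 × 0.29 = 0.039, or 3.9 points.
- Individual randomisation: 0.20 × 0.693 × 0.71 × 0.29 = 0.029, or 2.9 points.

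Week allocation therefore adds about 1 point. The ordinary standard error of the difference is √[(0.621 × 0.379 + 0.80 × 0.20)/50] = 0.089, or 8.9 points, and it already covers the individual-randomisation part.

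**4. Precision for Aim 2.** Simulated trials with 50 per arm and 62.1% v 80% compare the variance of the adjusted risk difference with that of the unadjusted one:

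| Assumed age effect | Adjusted / unadjusted variance |
|---|---|
| None | 1.02-1.03 |
| Keenoa arm only | about 1.00-1.02 |
| Both arms equally, OR 2.0 per SD | 0.94-0.89 |
| Both arms equally, OR 2.5 per SD | 0.89-0.82 |

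In the last two rows the first figure is without week clustering of age and the second is with 5% of age variance between weeks.

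**5. Precision for Aim 1.** The equivalent gain in participants is 1/(1 − R²) − 1. This is 5.3% at R² = 0.05 and 25% at R² = 0.20, both values assumed.

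**6. Error rate of the participant-level test.** With one prognostic covariate at log-odds 1.0 per SD and 10% of its variance between weeks, simulated type I error is 7.9% unadjusted and 4.9% adjusted. At log-odds 0.5 it is 6.2% and 5.3%. Adjustment removes only the part that the covariate explains. For residual outcome clustering the design effect is 1 + 15.67 × ICC, or 1.16 at ICC 0.01 and 1.78 at 0.05. The naive type I error is then 6.8% and 14.2%.

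**7. Cost of week-level inference.** Six weeks less two means leaves 4 degrees of freedom. The critical value is 2.78 instead of 1.96, so intervals are 2.78/1.96 = 1.42 times as wide for the same standard error.

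**The case against.** An unadjusted primary comparison is permissible in a randomised trial, and chance imbalance does not bias it in expectation. This stands. The invalid element is the participant-level standard error under week allocation, and covariates cure that only in part.

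The natural rationale for age, ease with a phone app, applies mainly to the Keenoa arm. On that mechanism the gain is essentially nil. This also stands. The larger gains need an age effect of similar size in both arms, for which the documents offer no evidence. A cohort of older adults may span a narrow age range, which would weaken age further, and nothing in the documents singles out sex.

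Three stronger readings are tempting and are not supported:
- That week allocation threatens a 4-point distortion, over a fifth of the planned 17.9. Most of that figure (2.9 of 3.9 points) would arise under individual randomisation, and the odds ratio and the between-week share are both assumed.
- That adjustment is free. It loses 2-3% of precision if age is unrelated to outcome.
- That adjustment rescues the power. From 50.5% it rises only to 52.6% at R² = 0.05 and 59.9% at R² = 0.20. An R² of about 0.50 would be needed to reach 80% at 50 per group.

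A week-level test on 4 degrees of freedom may also cost more than adjustment gains. That is so, but it is the price of the allocation scheme, and the participant-level test avoids it only by ignoring how the tool was allocated.

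**Conclusion.** The point holds in limited form. Both tests are unadjusted, characteristics are only described, and six weeks are randomised; none of this depends on an assumption. It follows that between-week differences in case mix are neither adjusted for nor reflected in the standard errors.

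The size of the benefit is not established. Every precision figure depends on an age-outcome association that the documents do not report, and the range includes a small loss. Pre-specified adjustment is worth having because it needs no new participants and removes discretion after the characteristics table is seen. It accompanies a week-level analysis and does not replace one.

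A reader might infer that the planned result would be biased by age. The documents do not show that. Smartphone eligibility is described only for Keenoa weeks, and any arm difference from that source would be systematic. It is a separate matter that this point does not settle.

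**What to change.** Amend the SAP as follows.
- **Covariates.** Pre-specify age (continuous) and sex in both comparisons. For Aim 1, use linear regression of the 0-5 score. For Aim 2, use logistic regression reported as a standardised risk difference with 95% CI.
- **Inference.** Name one analysis that respects week. Fit age and sex at participant level without the tool, average the residuals within each week, and compare the weekly means by tool on a t distribution with about 4 degrees of freedom. The p value and interval should come from this step.
- **Supporting result.** Keep the unadjusted comparison.

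This takes a few sentences and slightly more analysis, with no extra participants. The downsides are a possible 2-3% loss of precision and the wider week-level intervals. If the weeks split 3:3, which the documents do not state, there are only 20 possible allocations. An exact two-sided randomisation test could then not go below 2/20 = 0.10, so the week-level p value relies on the t approximation. The sample size needs its own correction.
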